## Arm 2 - Sit-Less: As described above for Arm 1, with the exception of:

After 1-hour post-breakfast the participants will complete a 3-minute bout of light-intensity walking, then return to the seated position. This procedure will be completed on a further 5 occasions at 30-minute intervals up to (and including) 3.5-hours post-breakfast. At 3.5-hours, the lunch meal will be consumed. At 1-hour post-lunch, (4.5-hours post-breakfast), and every 30-minutes thereafter up to and including 6.5-hours post-breakfast, a 3-minute bout of light-intensity walking will be performed (equalling 11x3 minutes bouts of walking; i.e. 36 minutes of light-intensity across the 7-hour day) (Figure 2). During the two 1-hour periods immediately following breakfast and lunch, participants will remain in a seated rested position to limit the risk of hypoglycaemia during peak insulin absorption time before commencing the 3-minute walking break on 60-minutes.

[figure not shown]
**Laboratory meals:** Both meals will seek to replicate a typical westernised diet with an energy density of ~855kcal and a macronutrient profile of ~42% energy from carbohydrate, ~16% energy from protein, and ~42% energy from fat. The carbohydrate content of each meal will equate 1g.carbohydrate.kg.BM. Each meal will contain ~40g of fat as this is typical of westernised dietary patterns and we have previously shown that meals with a similarly high fat content invoke an adverse response in postprandial glycaemic, lipaemic, and inflammatory parameters. The breakfast meal will comprise of cereal with milk and a slice of toast with jam and the lunch meal will comprise of a sandwich. Patients will be asked to consume each meal within a 20-minute window. Meals will be preceded by an insulin bolus, calculated from each participant's usual insulin-to-carbohydrate ratio (with no correction dose), administered 10-minutes before eating, with those treated on MDI standardising insulin injection site. The timing and amount of water consumed with each meal, and ad libitum throughout the duration of the first visit will be recorded so that this can be replicated on subsequent visits.

Blood sampling: Periodic blood samples will be drawn at 60-minute intervals, for a total of 7-hours (commencing immediately prior to the consumption of the breakfast meal). At each time point, 10mL of venous whole blood will be taken and dispensed into Vacutainers before centrifugation at 3000 rev/min for 15-minutes at 4ºC. Plasma will be separated and stored at -80 degrees centigrade for retrospective analysis of insulin and triglycerides. At each time point, a panel of vascular inflammatory and thrombotic parameters, including plasma levels of C-reactive protein (CRP), complement C3, fibrinogen, plasminogen activator inhibitors (PAI)-1, interleukin 1b, will be assessed using standard ELISA techniques. CRP has been shown to predict future vascular events (ref), while C3 appears to have a role in both vascular inflammation and thrombosis potential, particularly in individuals with diabetes. Fibrinogen and PAI-1 levels can determine thrombosis risk in diabetes, and consequently predisposition to atherothrombotic disease. Moreover, recent work by the group has shown that lysis time of clots made from plasma samples is an independent predictor of cardiovascular mortality following coronary ischemia, and therefore we will study plasma clot formation and lysis using a validated turbidimetric assay. Work from the group has shown that fibrin clot lysis is impaired in people with T1D, representing one potential mechanism for the increased risk of vascular complications in this population. We have also shown that lowering glucose levels improves the hypofibrinolytic environment in diabetes, provided hypoglycaemia is avoided. An additional 5mL of venous blood will be taken at rest on one arm of the study for C-peptide and routine blood tests (including HbA1c, U&Es, LFTs, full lipid profile, urinary albumin creatinine ratio (unless these have been done within three months of enrolment). A total of 8 blood samples will be taken across the course of each study visit equating to a total of 85ml, which is approximately 1/5 of a full blood donation. The total volume of blood to be taken is safe, and, is similar to other studies that we have performed previously in people with T1D. Further, we have worked hard with our PPI representatives to minimise the participant burden of all study procedures; the volume and frequency of blood sampling has been deemed acceptable by our PPI representatives.

### Post-laboratory observation period:

Following the last blood sample at 7-hours post-breakfast, participants will be discharged from the laboratory. Glycaemia will continue to be monitored under free-living conditions for a total of 48-hours post-intervention using CGM. As we are interested in the 48-hour glucose responses following our intervention (including the dawn phenomenon), participants will be given two standardised meals to consume as their evening meal and breakfast, and be required to replicate their dietary intake across trials

for the duration of the 48-hour post-intervention period, in order to control for the potentially confounding effects of diet on glycaemic control. This will provide the unique opportunity to investigate the legacy effects of interrupted sitting on glycaemic parameters, including the dawn phenomenon.

### Data analysis:

Standard summary statistics of the CGM data for each condition will be calculated, including: mean CGM glucose, percentage of time spent within euglycaemia, hyperglycaemia, and hypoglycaemia; area under the curve (a measurement of participants' exposure to euglycaemia, hyperglycaemia, and hypoglycaemia levels over time) for all glucose measurements that exceed a threshold of 10 mmol/L or 6.9 mmol.L, and fall below thresholds of 3.9 mmol/L or 2.8 mmol/L; number of hyper- and hypoglycaemic excursions; glycaemic variability. Functional data analysis will be performed as previously detailed to generate temporal profiles for each measurement period.

Online nutrition analysis software (MyFood 24, Dietary Assessment Ltd), and accelerometer software (activPAL3TM, Activeinsights) will be used to determine the composition and nutritional content of pre-laboratory 24-hour dietary intakes and accelerometer data, respectively; as dietary intake and physical activity levels will be replicated across experimental visits and are not an experimental outcome, no formal statistical analysis will be undertaken.

# Sample size:

Our sample size calculation is based on our preliminary data and primary outcome variable of mean 48-hour interstitial glucose assessed using FDA. Owing to the randomised crossover design of our study, participants will act as their own controls, which enhances both the internal validity and reliability of the data collected and permits a smaller sample size. To detect a significant difference in mean interstitial glucose of 1.6mmol/L with a SD of 1.5 (effect size 0.64) at P <0.05 with 95% power we will require a sample size 32. This is a clinically relevant effect size in people with diabetes; improving CGM glucose by this small, but clinically relevant margin in T1D has been shown to result a reduction of HbA1c by 1.0mmol/mol over the long-term^76. We have shown greater improvements in interstitial glucose in people with T2D in response to interrupted sitting interventions. This number of individuals is enough to detect a 26% difference in clot lysis time with a power of 90% given SD of the variable studied at 22%. This difference in lysis time reflects 18% lower risk of cardiovascular mortality in individuals with acute coronary syndrome, as we demonstrated in our recent study.

Vascular inflammatory, thrombotic and platelet responses: As these are exploratory outcomes with no previous data available on how activity breaks affect platelet biology in T1D it is difficult to provide a formal power calculation. Previously we have infused lipids into healthy subjects and then examined platelet function. In this study we found significant differences in platelet function pre- and post-lipid infusion using 20 healthy participants; as the biochemical abnormality is assumed to be higher in T1D individuals we are confident that our sample size of 32 will be adequate to detect a meaningful difference in our vascular inflammatory, thrombotic and platelet measures.

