### STUDY PROTOCOL:

Study Design: A single-centre, randomised and counter-balanced, two-arm cross-over study.

**Population:** 32 adults with T1D aged between 18-70 years. Age is restricted to a minimum of 18 years due to the well documented hormonal effects on glycaemic control in adolescents and young adults.

**Inclusion criteria:** A diagnosis of T1D for a minimum of 5 years; Currently treated on a stable insulin regimen for a minimum of 6 months consisting of continuous subcutaneous insulin infusion (CSII) therapy or multiple daily injections (MDI) of a combination of rapid-acting and long-acting insulin; Familiar and currently using the carbohydrate-counting method for determining mealtime insulin dose; Not currently pregnant; No overt diabetes complications including end stage renal failure requiring dialysis; Free from hypoglycaemia unawareness assessed through a combination of the Clarke and Gold methods; No recent (<6-months) history of diabetic ketoacidosis (DKA); Free from medical conditions relating to a haematological disorder, gut mobility or digestion; No history of anorexia, bulimia, or any other disordered eating; No history of deep vein thrombosis; No history of heart attack or stroke within 6 months prior to recruitment; No history of malignancy; No existing medical or psychiatric conditions likely to interfere with the study; No severe functional limitations that contraindicate prolonged episodes of sitting (i.e. back pain) or short frequent bouts of light-intensity walking (i.e. mobility issues); No dietary allergies or intolerances likely to interfere with the study; Able to understand written English and provide written informed consent; Do not currently meet the recommendations for moderate-to-vigorous physical activity (150 min/wk) in adults.

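### The stated difference (1.6 mmol/L) and SD (1.5) give an effect size of 1.07, not the 0.64 that produces n = 32, so the glucose difference the trial is sized for is unclear

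*Protocol*

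**What the plan says.** The Sample size section of the protocol names the "primary outcome variable of mean 48-hour interstitial glucose assessed using FDA" as the basis of the calculation. It relies on pairing: "Owing to the randomised crossover design of our study, participants will act as their own controls". It then sets out the inputs as a "difference in mean interstitial glucose of 1.6mmol/L with a SD of 1.5 (effect size 0.64) at P <0.05 with 95% power" and concludes "we will require a sample size 32". The population paragraph at the start of the protocol gives the same number, "32 adults with T1D aged between 18-70 years".

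The sentence that follows the calculation describes the effect as clinically relevant and links it to a long-term fall in HbA1c. The section does not say whether the SD is that of the within-person difference or of glucose under one condition. It gives no within-person correlation, does not say whether the test is one- or two-sided, and names no test or formula.

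**The concern.** A standardised effect size is a difference divided by an SD. The sentence prints all three quantities, and they do not agree: "difference in mean interstitial glucose of 1.6mmol/L" over "with a SD of 1.5" is not "effect size 0.64". At least one of the three is wrong, or the SD is of a kind the text does not describe.

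At stake is what the trial is designed to detect. The difference and the SD are the two inputs with a clinical meaning. If the SD of within-person differences really is 1.5 mmol/L, then 32 participants are enough for a difference of about 1.0 mmol/L and far more than enough for 1.6. If 1.6 is the real target and 0.64 the real effect size, then the SD is understated by 1.0 mmol/L. The argument for clinical relevance follows directly on the 1.6, which may not be the difference for which 32 was calculated.

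**Working it through.** **Inputs (Protocol, Sample size):** difference 1.6 mmol/L; SD 1.5; effect size 0.64; significance level 0.05; power 95%; n = 32; crossover with each participant as own control. Two-sided testing is assumed, because the text does not state it.

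**Step 1. Reproduce n = 32 from the stated effect size.** For a paired comparison, n = ((z for alpha/2 + z for power) / d)².
- With d = 0.64: (1.960 + 1.645)² / 0.64² = 12.995 / 0.4096 = 31.7, so **32**. The protocol's figure is reproduced.
- The exact paired t-test (noncentral t) gives 34. Its power at n = 32 is 93.9%; the normal formula gives 95.2%.
- One-sided, d = 0.64 would give 27 (normal) or 28 (exact t).

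Effect size, alpha, power and n therefore agree with one another, apart from the usual small gap between the normal and t calculations.

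**Step 2. Effect size from the printed difference and SD.** 1.6 / 1.5 = **1.07**.
- n = 12.995 / 1.0667² = 11.4, so **12** (normal); **14** by exact t.
- One-sided: 10 (normal) or 12 (exact t).
- At n = 32, power for d = 1.07 exceeds 99.9%.

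**Step 3. Can another meaning of the SD rescue 0.64?** If 1.5 is the SD under one condition, the SD of the difference is 1.5 × √(2(1 − ρ)), where ρ is the within-person correlation.

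| ρ (assumed) | effect size | n, exact t, 95% power |
|---|---|---|
| 0 | 0.75 | 25 |
| 0.3 | 0.90 | 19 |
| 0.5 | 1.07 | 14 |
| 0.7 | 1.38 | 10 |

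To reach 0.64, the SD of the difference must be 1.6/0.64 = 2.5. Then 2(1 − ρ) = (2.5/1.5)² = 2.78, so ρ = **−0.39**. A negative correlation contradicts the section's own argument that using participants as their own controls permits a smaller sample.

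**Step 4. Can a parallel-group formula explain it?** Two-sided at 95% power, d = 0.64 needs 64 to 65 per group and d = 1.07 needs 23 to 24 per group. Neither gives 32 per group or 32 in total.

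**Step 5. Which pairs give 0.64?**
- Difference 1.6 with SD 1.6/0.64 = **2.5**.
- SD 1.5 with difference 0.64 × 1.5 = **0.96**.

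**Step 6. What 32 participants detect if the SD of differences is 1.5.** By the normal formula the detectable effect size at 95% power is 3.605/√32 = 0.637, which is 0.637 × 1.5 = 0.96 mmol/L. By exact t it is 0.658, which is 0.658 × 1.5 = 0.99 mmol/L.

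**The case against.** The best defence is that the sample size itself stands. The 0.64 gives 32 by a standard formula, so the calculation was probably run correctly and one clinical input was then misprinted. That defence is right as far as it goes. A reader might infer that the whole statement is impossible and that neither effect size gives 32; Step 1 shows otherwise. The exact-t figures of 34 and 93.9% reflect a choice between two accepted methods. The protocol names neither, so they are not an error in it.

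The consequence is also limited. With the printed SD of 1.5, under any non-negative correlation, no more than 25 participants are needed for 1.6 mmol/L.

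A reader might also take this sentence as the sole basis for the trial size. It is not: the same section says the number suffices for a 26% difference in clot lysis time at 90% power. Nor do the documents support a calculated power loss from dropout. They give no loss rate, and the CGM section provides for replacing a failed sensor.

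Sidedness and the type of SD could be left to an analysis plan. A stated ratio that contradicts its own numerator and denominator cannot, because the error is in the protocol's text. The sentence is intact running prose, and nothing else in the protocol resolves it.

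**Conclusion.** The point holds in a narrow form. The printed difference and SD give 1.07, while n = 32 rests on 0.64. The requirement at 95% power is 12 to 14 participants under the first and 32 to 34 under the second. The difference that 32 participants target is either about 0.96 to 0.99 mmol/L (SD of differences 1.5) or 1.6 mmol/L (SD of differences 2.5). The protocol does not show which. These figures assume a paired analysis, two-sided alpha of 0.05 and 32 completers.

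That 0.64 was the working input is an inference from its reproducing 32. An SD of 2.5 would reconcile every figure, but the document never states it.

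A reader might go further and infer that the trial is underpowered. If 2.5 were a per-condition SD, power for 1.6 would be 70% at zero correlation and 84% at 0.3. That requires an unstated SD, an unstated meaning for it and an assumed correlation, so the protocol does not support the conclusion. The primary power statement is wrong as written and must be corrected; the sample size of 32 is not shown to be wrong.

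**What to change.** Return to the preliminary data and restate one consistent set: the difference, the SD of the within-person difference (labelled as such), their ratio, two-sided alpha, the formula or test used, and power at n = 32.

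- **If the SD of differences is 1.5:** state that 32 completers give 95% power for about 0.96 mmol/L (normal formula) or 0.99 mmol/L (exact t), and over 99.9% for 1.6. Justify the clinical relevance of that smaller difference, since the present argument is attached to 1.6.
- **If 1.6 and 0.64 are right:** correct the SD of differences to 2.5 and state the power as about 94% (exact t) to 95% (normal formula).

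The cost is a rewrite of the sample-size paragraph and a check of the pilot data. Neither branch needs extra participants or a change of design.
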